### 4.1. Overall Design

- Study 200894 is a double-blind, double-dummy, randomized, parallel group, placebo-controlled superiority study. The study will be conducted as a collaboration between the Eijkman Institute of Molecular Biology (Jakarta), Eijkman Oxford Clinical Research Unit (within the Eijkman Institute, Jakarta), Faculty of Medicine, University of Indonesia (Jakarta) and the Indonesian army. The protocol will require appropriate ethics committee approval.
- Approximately 150 subjects will be enrolled from the Indonesian army returning from deployment in a heavily malarious region of Indonesia (e.g. Papua) and diagnosed with *P. vivax* malaria based on microscopic examination (confirmed by a second microscopist).
- Informed consent process: Research team leaders will meet commanders and the troops to explain the concept and importance of voluntary informed consent prior to inviting subjects to participate in the study. Subjects will give written informed consent prior to any screening assessments being undertaken. The written consent will be obtained by a site team member who is independent of the subject (i.e. not the subject’s commander or supervisor) and the voluntary nature of the study will be emphasised (See Section 7.2).
- At Day 1, subjects will be screened for G6PD deficiency using a suitable Point of Care Test (e.g. Fluorescent Spot Test) in order to exclude those who are G6PD deficient (See Study Reference Manual, SRM). G6PD deficiency will also be assessed by a quantitative spectrophotometric assay but the results will not be available at the time of randomization. If results are discordant, the subject will be reviewed and appropriate G6PD testing will be repeated.
- Subjects who have undergone screening and meet the label requirements for DHA-PQP dosing can receive open label DHA-PQP if the clinician deems that appropriate and at least 3 hours have elapsed since last food intake. Thus, DHA-PQP may be commenced whilst the results of the hematology, clinical chemistry or G6PD deficiency screening tests are pending. Once all laboratory evaluations are available and subject eligibility is confirmed, they will be randomized to blinded study treatment on a 1:1:1 basis. The first dose of blinded study treatment will be administered with food at least 3 hours after dosing with DHA-PQP, on Day 1 or Day 2 (see Section 7.2).

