## **9. STATISTICAL CONSIDERATIONS AND DATA ANALYSES**

### **9.1 Hypotheses**

The study is designed to test superiority of DHA-PQP plus TQ against DHA-PQP alone in the prevention of *P. vivax* malaria relapse. The null hypothesis for the primary endpoint is that the 6-month relapse-free efficacy is not different between the DHA-PQP plus TQ and DHA-PQP alone treatment groups. The alternative hypothesis is that the relapse-free efficacy of the treatments is different. The hypothesis test will be two-sided and tested at the 5% significance level.

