### **9.2 Sample Size Considerations**

#### **9.2.1 Sample Size Assumptions**

The sample size for the study is based on the comparison of the primary endpoint (i.e. relapse-free efficacy at 6 months post-dosing) between the DHA-PQP alone group versus DHA-PQP plus TQ. The comparison will be based on a Log rank test for the difference in relapse-free survival rates over 6 months using all the subjects in the intent to treat population.

It is assumed that the relapse-free efficacy will be 50% on DHA-PQP alone, 85% on DHA-PQP plus PQ, and 85% on DHA-PQP plus TQ. In order to detect a clinically meaningful difference of 35%, a sample size of 50 subjects per group will provide >90% overall power for the primary efficacy comparison, allowing for a 10% withdrawal rate. A trial of 150 subjects, with the given assumptions about DHA-PQP, DHA-PQP plus PQ, and DHA-PQP plus TQ relapse rates would expect to see 40 relapses: a combined relapse rate across all treatments of 26.7%. In addition, a DHA-PQP plus PQ arm will be used as a benchmark to help further interpret the observed relapse efficacy of DHA-PQP plus TQ.

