2. SUMMARY OF KEY PROTOCOL INFORMATION

2.1. Changes to the Protocol Defined Statistical Analysis Plan

Gastrointestinal (GI) tolerability was listed as an endpoint in the protocol. Data from phase 3 studies of tafenoquine, reported since the protocol was finalised, have abated previous concerns with regards GI tolerability, and hence this endpoint will not be specifically analysed. GI AEs will however still be reported in summaries of adverse events (AEs).

Additional study populations have been defined:

The Safety Open Label, Primaquine phase, Non-Relapsers (Safety OL) Population, has been defined for the summaries of adverse events for the participants who did not relapse during the double-blind phase and went onto the open-label primaquine phase at the end of the study.

The PK population has been defined as all participants for whom at least one systemic tafenoquine concentration, and associated sample date/time is available.

The ITT population has been renamed to the microbiologic-intent-to-treat population (mITT) and the definition updated to include the need for participants to have microscopically-confirmed *P. vivax* parasitemia at baseline.

The primary analysis uses a Cox's proportional hazards model as opposed to the log rank test as described in the protocol.

At the time of finalising the full RAP, it had been established that a blinded data review was not required due to 150 participants having been randomised. Details of the blinded data review are therefore not included in the RAP. It was also known that recruitment was from 2 battalions.

For the analysis of dichotomous endpoints, logistic regression analysis will be performed as opposed to exact methods as defined in the protocol. This enables battalion to be adjusted for in analyses.

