Endpoint / Variable
Percentage of participants relapsing by CYP2D6 genotype – Activity Score
Model Specification
mITT population Logistic regression model adjusting for qualitative CYP2D6 Activity Score (AS) within treatment arm (models fitted separately for each treatment arm)
Model Checking & Diagnostics
Goodness of fit tests and residual plots (pearson and deviance residuals to detect outliers and/or influential points) will be produced.
Model Results Presentation
Degrees of freedom, wald chi-square and p-value of the type III effect of AS in the model
Subgroup Analyses
No subgroup analyses are planned for this endpoint.

Sensitivity and Supportive Analyses

No sensitivity analyses are planned for this endpoint.

Additional Efficacy Summaries

P. vivax asexual parasite counts (Table 2.1), mITT population:
Summary statistics (n, median, Q1, Q3, min and max) at each timepoint by treatment group.

Other malarial asexual parasite counts (Table 2.2), *P. vivax* gametocyte counts (Table 2.3), other malaria gametocyte counts (Table 2.4), mITT population:
Summary statistics (n, median, Q1, Q3, min and max) at each timepoint by treatment group.

Summary of participants with *P. vivax* gametocyte emergence post baseline (n, %), mITT population, by treatment group.

Summary of participants with *P. falciparum* asexual parasite emergence post baseline (n, %), mITT population, by treatment group.

Summary of the number of relapses per subject (n, %), mITT population, by treatment group.

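### CYP2D6 activity score: if it enters as an unordered class variable, as the SAP most naturally reads, the Wald test has almost no power in the tafenoquine and primaquine arms

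*SAP*

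**What the plan says.** SAP 7.3.5 has two exploratory CYP2D6 analyses of relapse. The one at issue is the Activity Score analysis: a "Logistic regression model adjusting for qualitative CYP2D6 Activity Score (AS) within treatment arm", with a separate model for each arm. The planned output is "Degrees of freedom, wald chi-square and p-value of the type III effect of AS in the model". No odds ratio or confidence interval is listed. Table shell EFF_T8 (Table 2.24) has the same three columns, adds battalion to the model and states that the p-value is two-sided.

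SAP 11.6.3 sums two allele values, so the score can be 0, 0.5, 1, 1.5, 2, or 2.5 and above. For the companion metabolizer-class model, the SAP pools classes because poor and ultra metabolisers are few. It does not pool score levels. For the score model it gives no rule for separation, no penalised or exact method and no sensitivity analysis.

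On numbers, Protocol 9.2.1 states: "It is assumed that the relapse-free efficacy will be 50% on DHA-PQP alone, 85% on DHA-PQP plus PQ, and 85% on DHA-PQP plus TQ". It plans 50 per group with 10% withdrawal. SAP 2.1 records that no blinded review was needed "due to 150 participants having been randomised".

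**The concern.** The hypothesis in Protocol 4.1 is ordered and directional: people with absent or intermediate CYP2D6 metabolism should relapse more on PQ, but not on TQ. A type III test of a qualitative factor discards the order, and a two-sided test discards the direction.

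With few relapses, a score level may contain no relapse, or only relapses. The maximum likelihood estimate for that level is then infinite and its Wald standard error becomes very large, so the level adds a degree of freedom but almost nothing to the chi-square. Goodness-of-fit tests and residual plots do not repair this.

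Table 2.24 would print a p-value with no estimate beside it. A reader could not see that the fit had broken down, and could take a large p-value in the PQ arm as evidence against a CYP2D6 effect.

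**Working it through.** **Inputs.** Relapse rates of 15% (TQ), 15% (PQ) and 50% (DHA-PQP only), with 50 per arm or 45 after 10% withdrawal (Protocol 9.2.1). Allocation 1:1:1 (Protocol 4.1). Six possible score values (SAP 11.6.3). The score distribution is not in the documents, so it is assumed below.

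**1. The plan's own figures.** Expected relapses: 0.50×50 + 0.15×50 + 0.15×50 = 25 + 7.5 + 7.5 = 40, and 40/150 = 26.7%, as stated. Power of the primary comparison: hazard ratio ln(0.85)/ln(0.50) = 0.2345; events 45×(0.50+0.15) = 29.25.
- Schoenfeld: √(29.25/4)×|ln 0.2345| − 1.96 = 1.96, so 97.5%.
- Freedman: √29.25×(1−0.2345)/(1+0.2345) − 1.96 = 1.39, so 91.8%.

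Both agree with the stated power above 90%. No power or event count is given for the CYP2D6 models.

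**2. Events per model.** TQ and PQ: 0.15×45 = 6.75 to 0.15×50 = 7.5 each. DHA-PQP only: 0.50×45 = 22.5 to 0.50×50 = 25. Protocol 2.1.4 cites relapse below 10% over 12 months on DHA-PQP plus PQ; 0.10×50 = 5, so the PQ arm could have fewer than 5. A class factor with 4 to 6 levels needs 3 to 5 parameters.

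**3. Chance of a level with no relapse.** Seven relapses spread over k equally likely levels, no effect: 1 − (assignments reaching every level)/k⁷.
- k=3: 1 − 1806/2187 = 17%
- k=4: 1 − 8400/16384 = 49%
- k=5: 1 − 16800/78125 = 78%
- k=6: 1 − 15120/279936 = 95%

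Unequal levels or a real effect raise these. At 15% relapse, a level of n participants is all-or-none with probability 0.85ⁿ + 0.15ⁿ: 74.5% for n=2, 61.7% for n=3, 44.4% for n=5.

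**4. Simulation.** 600 arms of 50 per row; class score plus battalion; joint Wald test at 5%. The trend test is a permutation test on the numeric score. The effect is an odds ratio (OR) for score ≤1 versus >1, with the arm's relapse rate held fixed. Assumed shares for scores 0, 0.5, 1, 1.5, 2, ≥2.5:
- A: 2/8/35/25/28/2%
- E: 2/3/15/20/57/3%
- D: 0/10/35/25/30/0%
- C: 0/0/40/30/30/0%

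Cells show separated / Wald rejects / trend rejects, in %.

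| Distribution | OR | 15% relapse (TQ, PQ) | 50% relapse (DHA-PQP only) |
|---|---|---|---|
| A, six levels | 1 | 94.0 / 0.0 / 3.2 | 80.2 / 0.8 / 3.8 |
| | 5 | 96.0 / 0.2 / 34.5 | 84.3 / 26.2 / 62.5 |
| | 10 | 97.5 / 0.7 / 47.7 | 88.0 / 49.8 / 90.5 |
| E, six levels | 1 | 96.5 / 0.2 / 4.3 | 87.5 / 0.0 / 4.7 |
| | 5 | 94.8 / 4.0 / 37.2 | 93.7 / 1.2 / 36.3 |
| | 10 | 96.2 / 7.5 / 63.7 | 94.2 / 2.5 / 58.7 |
| D, four levels | 1 | 63.0 / 0.2 / 6.3 | 16.2 / 1.0 / 6.2 |
| | 5 | 74.0 / 2.2 / 33.5 | 27.3 / 41.8 / 64.2 |
| | 10 | 87.5 / 2.3 / 51.7 | 39.3 / 77.2 / 92.2 |
| C, three levels | 1 | 24.8 / 1.3 / 4.0 | 0.0 / 2.8 / 3.2 |
| | 5 | 56.8 / 4.5 / 36.0 | 1.3 / 62.0 / 60.8 |
| | 10 | 76.3 / 5.5 / 63.5 | 4.8 / 87.2 / 88.2 |

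Wider runs (45 or 50 per arm, with and without battalion, also an OR of 5 per unit of score) gave, at 15% relapse:
- separation with 4-6 levels: 63-97% with no effect, 69-98% with an effect;
- separation with 3 levels: 23-29% and 50-81%;
- Wald power: 0.1-4.5% at OR 5 and 0.2-10.5% at OR 10;
- one-degree-of-freedom trend test: 29-65% and 52-69%.

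Runs with an ordered effect, OR 2-3 per 0.5 step, gave 65-97% separation with 4-6 levels, 26-66% with 3, Wald power 0.3-4.7% and trend power 22-75%.

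**5. Source of the loss.** For distribution E at 15% relapse and n=50, a likelihood-ratio test of the same class factor has 33.1% power at OR 5 (Wald 3.3%, trend 44.0%) and 58.3% at OR 10 (Wald 10.5%, trend 68.9%). There, most of the loss comes from using a Wald statistic on a separated fit, and less from the class coding itself.

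**6. Is the p-value forced to 1?** Take levels of 8, 12, 14 and 16 with 5, 1, 1 and 0 relapses. The logits of the first three are 0.511, −2.398 and −2.565, with variances 0.533, 1.091 and 1.077. The fourth has weight tending to zero. The weighted mean is −0.974 and the Wald chi-square is 4.13 + 1.86 + 2.35 = 8.34 on 3 df, p = 0.039. A separated fit can still reject.

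**The case against.** **Class coding is an inference.** The SAP never says that the score is a class variable. The activity-score paper it cites uses the word qualitative in its own title, and shell EFF_T7 prints the same df, chi-square and p-value columns for baseline parasite count, which SAP 7.1.5.1 treats as continuous. This stands. If the score is numeric, separation largely disappears and the linear term is already planned; the text then only needs to say so. Qualitative together with a type III effect still makes class coding the natural reading.

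**The companion model covers the hypothesis.** The pooled metabolizer-class model (Table 2.23) gives counts, an odds ratio, a 90% CI and a one-sided test. At active-arm event rates it was separated in only 4-8% of samples under four of five assumed distributions, and in 22-25% under the fifth. This stands as partial mitigation, since a reader has an interpretable estimate next to Table 2.24.

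**The remedy is not powerful either.** About 7 relapses left the trend test below 80% power in every active-arm scenario run, and linearity is an assumption that class coding avoids. Both are true, but the choice is between low power and almost none.

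**Stronger readings.** A reader might infer that all three models rest on about 7 relapses; the DHA-PQP only arm expects 22.5-25. A reader might infer that separation drives the p-value to 1 whatever the truth; the example in the working gives 0.039. A reader might infer that separation is certain; with three common levels and no effect it occurs in about a quarter of samples.

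**Conclusion.** The point holds for the TQ and PQ models if the score is class-coded. Separation is likely: about 65-97% of samples with four to six levels and about 25-65% with three, rising to 81% in the strongest scenario run. Wald power is roughly 0-10% even for strong effects, against roughly 20-75% for a one-degree-of-freedom trend test. With no effect the Wald test rejects in only 0-1.3% of samples, well below its nominal 5%.

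The DHA-PQP only model is less affected. Class coding loses power there under the four- and six-level distributions, but with three common levels the two tests perform alike.

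These ranges rest on assumed score distributions. The SAP's remark that poor and ultra metabolisers are few points towards sparse extreme levels but does not fix the numbers.

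The consequence is limited: a non-significant score p-value in Table 2.24 would say almost nothing about the CYP2D6 hypothesis. The documents do not support extending this to the primary or secondary efficacy results, or to the whole CYP2D6 question, because the pooled two-class model remains. This is an inexpensive improvement to an exploratory analysis.

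**What to change.** In SAP 7.3.5 (Activity Score), state that the score enters as a single ordered linear term. Estimate it by Firth penalised likelihood, with profile-likelihood rather than Wald inference, or use an exact trend test. In Table 2.24 report the odds ratio per 0.5 unit with its CI, and show relapse counts by score level and arm.

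Reconcile the model text, which has no battalion term, with shell EFF_T8, which includes one. Adding battalion cannot remove separation.

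The cost is about one line in the SAP and a small change to one table shell. The downside is a linear-trend assumption in an exploratory model; the counts by level let a reader judge it.

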8. SAFETY ANALYSES

The safety analyses will be based on the Safety and Safety OL populations, unless otherwise specified.

8.1. Adverse Events Analyses

Adverse events analyses including the analysis of adverse events (AEs) and Serious (SAEs) will be based on GSK Core Data Standards. The details of the planned displays are provided in [Appendix 11: List of Data Displays](#).

In addition to the standard displays the following study specific tables will be produced:

Summary of protocol-defined SAEs (Hb drop). Hb drops will be identified from the SAE page of the eCRF and confirmed by laboratory data. The laboratory data will be checked during programming to ensure there were no protocol-defined SAEs that were not reported as such.

Summary of grade 3 and grade 4 AEs.

AEs related to drug will be identified as either related to DHA-PQP or related to blinded study medication, per the 'Relationship to Investigational Product' flag in the eCRF.

8.1.2 Overview of Planned Adverse Event Analyses

Counting of AEs will be based on the number of participants – not the number of AEs. For example, if a participant reports the same AE on three occasions within the relevant time interval, that AE will only be counted once. If a participant experiences the same AE (i.e. same preferred term) more than once, they are counted only once under the count for the preferred term. If a participant experiences more than one AE in a SOC, they will only be included once in the count for the SOC, but will appear in the count for each appropriate preferred term within the SOC. Therefore, the sum of the numbers of participants with each preferred term event within a SOC may exceed the total number of participants with at least one event. For the summary of AEs by maximum intensity, participants who experience the same event several times with different intensity will only be counted once with the maximum intensity.

The recurrence of *P. vivax* malaria and any associated signs and symptoms are recorded as Disease Related Events (DREs) and will not be included in the AE data displays, but will be listed separately.

Adverse Events will be summarized by treatment group and as specified in [Appendix 11](#) and presented in order of descending frequency. The tables presented using the Safety Population will be presented from administration of first study medication (including DHA-PQP) until Day 180.. The tables presented using the Safety OL population will be presented from Day 180 visit + 1 day until Day 180 visit + 21 days.

8.2. Adverse Events of Special Interest Analyses

Categories for AEs of Special Interest are defined in Section 11.6.4.

A comprehensive list of MedDRA terms based on clinical review will be used to identify each type of event. Changes to the MedDRA dictionary may occur between the start of the study and the time of reporting and/or emerging data may highlight additional adverse events of special interest (AESIs), therefore the list of terms to be used for each event of interest and the specific events of interest will be based on the safety review team (SRT) agreements in place at the time of reporting. AESIs will be identified prior to the unblinding of the study. The details of the planned displays are provided in [Appendix 11: List of Data Displays](#).

8.3. Clinical Laboratory Analyses

Laboratory evaluations including the analyses of Chemistry laboratory tests, Haematology laboratory tests, Urinalysis, and liver function tests will be based on GSK Core Data Standards. The details of the planned displays are in [Appendix 11: List of Data Displays](#).

In addition to the standard displays the following study specific displays will be produced:

Tables:

Summary of clinical chemistry / haematology abnormalities defined as values outside of the clinical concern range as defined in Section 11.8.1.

Summary of haemoglobin categories of change from baseline (categories defined as ≤ 20 g/L, > 20 g/L to ≤ 30 g/L, > 30 g/L).

Summary of haemoglobin declines over the first 28 days (categories defined as ≤ 20 g/L, > 20 g/L to ≤ 30 g/L, > 30 g/L or $\geq 30\%$).

Figures:

Maximum absolute methaemoglobin value over 28 days

Change from baseline in methaemoglobin over time

Data recorded at unscheduled assessments will not be included in tables and figures but will be listed, unless it fits into a visit window per Section 11.3.1.

8.3.1. Haemoglobin Declines and Related Laboratory Parameters

If a participant has a > 30 g/L decline from baseline haemoglobin or is found to be G6PD deficient, a haematological profile plot will be produced for the participant (Figure 3.3). This will display their haemoglobin, reticulocytes (if available), methaemoglobin and bilirubin results (total and indirect bilirubin on same plot) at each visit. The participant

ID, treatment group, sex, age and G6PD status (quantitative assay) should be included as a header for each participant's plot.

8.4. Other Safety Analyses

The analyses of non-laboratory safety test results including ECGs and vital signs will be based on GSK Core Data Standards, unless otherwise specified. The details of the planned displays are presented in [Appendix 11](#): List of Data Displays.

In addition to the standard displays the following study specific tables will be produced:

Summary of QTcF values by category and visit. Categories for each post baseline timepoint are defined as:

Absolute QTcF:

≤450 msec

>450 to ≤480 msec

>480 to ≤500 msec

>500 msec

Increase from baseline QTcF:

0 to <30 msec

≥30 to <60 msec

≥60 and absolute QTcF≤480 msec

≥60 and absolute QTcF>480 msec

Summary of absolute and change from baseline in methaemoglobin

Details of blood transfusions will be listed.

Where triplicate assessments are performed (i.e. at baseline), the mean of the 3 assessments will first be derived and the summary statistics will be presented using the mean of the assessments. For categorical data, e.g. ECG findings, the worst case should be presented where data is taken in triplicate.

9. PHARMACOKINETIC ANALYSES

PK analyses will be the responsibility of Clinical Pharmacology Modelling and Simulation within GSK.

A sparse sampling scheme has been employed in the study. Predictive checks will be performed based on the existing TQ POPPK model developed with data from the Phase 3 studies. With adequate predictive performance, the model will be utilized to generate the post hoc PK parameters for individual participants from the current study. These PK parameters will then be utilized to characterize their systemic exposure.

In case of lack of fits between model predictions and observed data, the existing model developed with Phase 3 data may be adjusted to characterize TQ PK. In this scenario, the tafenoquine systemic concentration- time data will be utilized in a population PK analysis to estimate the fixed-effects parameters (including oral clearance (CL/F), volume of

distribution (V/F)) as well as the corresponding random effects (between- and within-subject variability) parameters as data permit.

In the event that the sparseness of the data does not support estimation of some PK parameters (e.g. rate of absorption), the model population parameters may be fixed to previously obtained parameter estimates from the population PK meta-analysis performed at the end of Phase 3 studies.

Additionally, if data permit, exploratory PK/PD analyses for TQ data may be undertaken to examine any relationship between PK parameters (e.g. systemic exposure) and/or clinical outcome (relapse-free efficacy) or safety parameters (e.g. change in QTcF or MetHb). Any exposure-response analyses based on emerging data will be described in detail in the study report.

Any deviation from the planned analysis will be described in detail in the study report.

